### **From the patients' perspective**

-the main definition will be for 'remission', PASS

-and as sensitivity analysis, patient-perceived remission or low disease single questions yes/no,

-and for flares, the GRAPPA flare questionnaire,

-and as sensitivity analyses, flare according to the patient (single question) and the assessment of worsening in MCID.

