## Objectives

- To define cutoffs of the most widely used composite scores (mixing physician assessment and PROs) and PROs, for disease activity levels corresponding to PsA remission/low disease activity and for change in level of disease activity corresponding to PsA flare, when remission/low disease activity and flare are defined from the patients' and physicians' perspectives.
- From the physicians' perspective, 'remission' will be defined by MDA and sensitivity analyses will use physician-perceived remission/low disease (single questions) and remission in composite scores (DAPSA, modified AMDF, PASDAS); flare will be defined as decision of treatment intensification and sensitivity analyses will use: global assessment of flare and increase in category of disease activity in the composite scores.
- From the patients' perspective, 'remission' will be defined as PASS attained and as sensitivity analysis, patient-perceived remission or low disease single questions yes/no, and flares will be defined using the GRAPPA flare questionnaire, and as sensitivity analyses, flare according to the patient (single question) and the assessment of worsening in MCID.

We will assess what 'physician-defined' remission/low disease/flare and patient-defined remission/low disease/flare correspond to both on composite 'physician' scores and on all the collected PRO scores. We will use cross-sectional data collected at baseline for remission and low disease activity; and changes in scores between the 2 visits for flares.

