#### *Flare*

Only flares at the time of assessment are targeted (and not recall of previous flares).

To assess flares from the patient perspective, the preliminary GRAPPA flare instrument will be evaluated: 1.A recent change in joint pain.2.A recent change in location of symptoms (i.e., sudden increase in pain or swelling in hands/feet).3.A recent change in the number of tender and/or sore joints. 4. A recent change in the

number of aching joints. 5. The presence or degree of pressure-sensitive joints. 6. A recent change/increase in the number of swollen joints. 7. A recent change/increase in night pain. 8. A recent change/increase in the number or combination of symptoms (**Table 1**). (Moverly2016a)

Patient will also answer a specific targeted question on their assessment of flare yes/no (see above).

The Minimum Clinically Important Difference (MCID) question gives information on change in disease status. The question is: "How would you describe your overall status since your last visit: much better, better, the same, worse, much worse?" Here, worse or much worse will be used to define a flare. (Curtis2015)

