### *Planned analyses*

Population: Analyses will be performed on all included patients with data available regarding the remission and flare status questions.

For remission, all included patients with data available regarding remission will be assessed. The primary analysis is on baseline data. The data from the second visit will be seen as confirmatory and will be analysed as longitudinal data accounting for multiple visits.

For flare, only patients with both visits completed will be used. Change in outcomes between the 2 visits will be assessed.

Similarly to what has been done in axial spondyloarthritis (and differently to what has been done in rheumatoid arthritis), it is decided that flare will be defined as a change in status between the 2 time points, i.e., a flare is an absolute or relative change between 2 values: the observed value of the outcome at the time of the flare, minus the referral value (previous status before the flare). (Gossec2016, Bykerk2016)

The patient's initial status (referral value of the outcomes at the first visit) may vary from no symptoms to moderate/high disease activity but we will analyse separately patients with very high initial values, since it is considered that definitions of flares are only relevant for patients initially not in very high disease activity.

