### Planned analyses:

Cutoff values for each outcome and for each change in outcome will be calculated using ROC curves and 75th percentile analyses (**Table 2 and 3**). For ROC curves, different cutoffs will be calculated, both using Youden's statistic (maximizing both sensitivity and specificity) but also using a fixed specificity number (80%) since specificity is more important than sensitivity in this case (to avoid overdiagnosing

flares). The 75th percentile technique is a classical technique which finds the value above which, 75% of patients reporting an outcome or a change in outcome, are placed. Rasch analysis will be used as appropriate. (Tubach2005, Machado2016) These techniques are widely used to determine cutoff values for continuous scores and are recommended by COSMIN (Mokkink2016/ website.cosmin)

Sensitivity analyses will explore cutoff values found according to patient demographic characteristics and country.

We will compare attainment of remission/low disease activity or flare according to the different definitions, using kappa analyses and logistic regression analyses will explore characteristics of patients who are in 'discordance' or not for flare/remission with the physician-defined definition, and physicians who are in 'discordance' with patients as well.

Missing data: All data will be analysed. To minimize missing data, the order of questions will also be studied to motivate respondents to finish the entire questionnaire.

**Table 2.** Planned analyses: defining cutoff values according to different definitions of remission/low disease activity (LDA)

Gold standards are below	MDA	Modified versions of MDA	Physician Gobal Assessment	DAPSA/c-DAPSA	PASDAS	Modified AMDF	PsAID	HAQ	Pain	Fatigue	PGA	SF12
MDA												
modified versions MDA												
Physician remission/LDA single questions												
Physician Global Assessment<4/10												
Composite score DAPSA												
Composite score PASDAS												
PASS												
Patient remission/LDA single questions												

**Table 3.** Planned analyses: defining cutoff values for change of outcomes according to different definitions of flare

Gold standards are below	MDA	Physician global ass.	DAPSA/c-DAPSA	PASDAS	Modified AMDF	GRAPPA flare questionnaire	PsAID	HAQ	Pain	Fatigue	PGA	SF12
Treatment intensification												
Physician flare single question												
Composite score DAPSA change in category												

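### Does the plan need a written positivity rule for the GRAPPA flare questionnaire, its main patient definition of flare?

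*Combined protocol and SAP*

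**What the plan says.** The Objectives state that, for patients, "flares will be defined using the GRAPPA flare questionnaire"; the section From the patients' perspective repeats this as "and for flares, the GRAPPA flare questionnaire". The single flare question and the MCID question serve as sensitivity analyses.

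The Flare section says that "the preliminary GRAPPA flare instrument will be evaluated" and lists 8 items. It gives no number of items, score or response format. For the MCID question the same section does give a rule: the two worst answers count as flare.

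On timing, the Flare section says "Only flares at the time of assessment are targeted". The Planned analyses section that sets out the populations says "it is decided that flare will be defined as a change in status between the 2 time points" and treats the first-visit value as "the referral value (previous status before the flare". It accepts initial states from no symptoms to moderate or high activity and adds that "we will analyse separately patients with very high initial values".

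Table 3 of the planned analyses, on "defining cutoff values for change of outcomes according to different definitions of flare", has the questionnaire both as a row (gold standard) and as a column (outcome). Table 1 collects it at both visits.

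**The concern.** The ROC, 75th-percentile and kappa analyses each need flare as yes or no. The main patient definition has no rule that produces it, while a sensitivity definition does. The Background says the questionnaire is not yet validated, so the documents offer no established threshold to fall back on.

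Two choices are open. The first is how many items make a patient positive. The second is whether flare means positive at the second visit or newly positive since baseline. The Flare section leans to the first reading and the Planned analyses section to the second, and they part for a patient who is positive at both visits. No inclusion criterion keeps such patients out.

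Both choices decide who is in the flare group and so move every patient-anchored change cutoff in the row. A threshold picked after looking at the data could be steered towards a preferred cutoff. Table 3 could also look circular, since the instrument serves as standard and as outcome.

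**Working it through.** **The plan's own figure.** Inputs from the Sample size section: SD of PsAID 2.30, 95% confidence, 82 patients in remission or flare. The formula n = (1.96 × SD / d)² with d = 0.5 gives (1.96 × 2.30 / 0.5)² = 81.3, rounded up to 82. The printed precision of 0.05 would give 8,129, so the working precision is ±0.5; that is a separate matter. Expected flares: 20% (Sample size) of 400 second visits (Budget) = 80.

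**Number of items (assumed model).** Eight items share one latent worsening factor; only worsening is counted. Mid-range inputs, none from the documents: each item endorsed by 30%, latent item correlation 0.6, between-visit PsAID correlation 0.7, correlation of PsAID change with worsening 0.6. SD of change = 2.30 × √(2 × (1 − 0.7)) = 1.78.

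| Rule | Flares per 400 | 75th-percentile cutoff | 80% specificity | Youden |
|---|---|---|---|---|
| at least 3 | 157 | −0.08 | 0.72 | 0.15 |
| at least 5 | 90 | 0.30 | 1.00 | 0.42 |
| rise | | 0.38 | 0.28 | 0.27 |

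At least 4 items gives 120 flares and a 75th-percentile cutoff of 0.11, so one step either way moves it by 0.19. Over 81 combinations of inputs (endorsement 20–40%, item correlation 0.4–0.8, between-visit correlation 0.5–0.8, correlation with worsening 0.4–0.8) the rises from 3 to 5 items are 0.12–0.96, 0.08–0.73 and 0.09–0.65.

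**Baseline positives (assumed model).** Mid-range inputs: 80 flares at visit 2, 60 baseline positives, 35% of them still positive (21), so 59 newly positive. Mean change is +1.5 if newly positive, 0 if the state is unchanged and −1.5 if resolved, with SD 1.78. Going from all visit-2 positives to newly positive only, with baseline positives set aside:
- 75th percentile: −0.17 to 0.30, a rise of 0.47
- 80% specificity: 1.37 to 1.50, a rise of 0.13
- Youden: 0.58 to 0.75, a rise of 0.17

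Across 108 combinations the 75th-percentile rise is 0.11–1.25. The 1.25 needs half of the 80 flares to be positive already at baseline, with a mean change of exactly 0 in that half and 2 in the other.

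**Yardstick.** The ±0.5 above is for the mean of a level. The 75th-percentile method takes the 25th percentile of change in the flare group. For normal data its half-width is 1.96 × √(0.25 × 0.75 / n) × SD / 0.318, where 0.318 is the standard normal density at that percentile. With n = 80 and SD 1.78: 1.96 × 0.0484 × 1.78 / 0.318 = 0.53. Using the first model's own flare counts and within-flare spread, it is 0.33 at 157 flares and 0.43 at 90. The mid-range shifts are therefore of the order of the sampling error or below it.

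**Dependence on the model.** A second simulation let the items reflect a mix of recent change and current level (between-visit correlation 0.6, endorsement 20% or 30%, squared loading 0.4 or 0.6). At least 4 items then gives a 75th-percentile cutoff of 0.88–1.54, against 0.11 above. Setting baseline positives aside raises it by 0.21–0.38. The direction agrees, but the cutoff differs between models by more than the mid-range shift within either one. The first two models are also not joined: 4 items gives 120 flares in the first, while the second fixes 80.

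**Table 3.** Of its 7 rows, 6 are other definitions of flare. The questionnaire column calibrates the instrument against those six, which fits the statement that it is to be evaluated. Standard and outcome coincide only in the diagonal cell. Table 2 has the same kind of cell (MDA by MDA).

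**The case for a change.** The strongest opposing case is that flare cutoffs are half of the stated objective, the main patient definition cannot be computed as written, and the authors wrote a rule for MCID in the same section. The shifts are systematic, so more patients do not remove them. In the mid-range case the 75th-percentile cutoff changes sign under either choice, so the rule could decide whether the flare cutoff is a worsening at all. The other definitions would reveal disagreement without saying which questionnaire rule was meant.

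Much of this stands. The rule is missing, and it has to be settled before the second-visit data are analysed and then reported. But the remedy that suggests itself is no firmer than the gap. A threshold of 4 of 8 items is a convention. A count from 0 to 8 assumes yes/no items, although one item is worded as presence or degree, and the CRF is not part of the documents.

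Taking every baseline positive out of the main analysis would go beyond the plan, which sets apart only very high initial values; nothing equates that with a given number of symptom items. It would also cost precision. With 40 to 72 flares left instead of 80, the half-width for a mean at SD 2.30 is 1.96 × 2.30 / √n = 0.71 to 0.53 instead of 0.50.

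**Conclusion.** The gap is genuine, but it is one that analysts fill, and it calls for no change to the plan. No written rule produces a wrong answer. The questionnaire row of Table 3 cannot be run without a definition, so the choice has to be made openly. On the visit, a plain reading of flare as a change in status already points to newly positive patients; a patient positive at both visits has not changed status. On the number of items, any figure written now would be a convention for an instrument the study itself sets out to evaluate.

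The consequences are limited by the plan's own framing. The section Outcomes and planned analyses says there is no gold standard and that several partial ones are used on purpose; the Sample size section calls the flare analysis exploratory.

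A stricter item count raises the cutoffs, and so does setting baseline positives aside, in every scenario examined. The mid-range sizes (0.27–0.38 and 0.13–0.47 PsAID points) rest on assumed item frequencies and correlations and are comparable with or below the sampling half-width of a 25th percentile. Larger shifts, up to 0.96 and 1.25, occur only at the edge of those assumptions. The documents give no item data that would narrow the range.

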### **Obtaining cutoffs**

We will assess what physician-defined remission/low disease activity/flare and patient-defined remission/low disease activity/flare correspond to both on composite 'physician' scores and on all the collected PRO scores (**Figure and Table 2**). We will use data collected at baseline cross sectionally for remission and low disease activity and changes in scores between the 2 visits for flares.

We will use data collected at baseline and at 1-6 months since flare is usually referred to as a change in disease status and indeed we are planning to define cutoff values for change in each outcome, corresponding to a flare.(Gossec2016)

Although we are aware the cutoff values obtained may differ between physicians and patients, we are not planning a reconciliation exercise.

### **Statistical analyses**

#### *Sample size*

The sample size is calculated to be able to determine the cutoff value of PsAID corresponding to remission or flare with a certain precision.

With a standard deviation of 2.30 as observed in the PsAID development study on 107 and 475 patients, with a confidence level of 0.95 and a precision of 0.05, it is necessary to analyse 82 patients in 'remission' (whatever the remission definition) or in flare. Since we expect around 20% of patients to be in remission in this usual practice cohort (given percentages of MDA are around 40-50% in randomised clinical trials of biological), and around 20% of patients to be in flare, we need to analyse a total of 410 patients for remission, thus we need to include 450 patients (taking into account uninterpretable CRFs due to missing data). (SAMPLE, Möttönen1999). For flares we are aware the sample size will be slightly smaller (taking into account patients having had a treatment intensification will not be assessed the second time), however for this exploratory analysis the sample size is considered sufficient for flares.

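### With an SD of 2.30, a precision of 0.05 needs 8,129 patients in the state, not 82; 82 patients give about ±0.5 PsAID points, and only for a mean

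*Combined protocol and SAP*

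**What the plan says.** The Sample size section (under Statistical analyses) gives its purpose as follows: "The sample size is calculated to be able to determine the cutoff value of PsAID corresponding to remission or flare with a certain precision". The variability input is "With a standard deviation of 2.30 as observed in the PsAID development study on 107 and 475 patients". The conclusion is that "with a confidence level of 0.95 and a precision of 0.05, it is necessary to analyse 82 patients", and this number is applied to remission under any definition and to flare. The section expects about 20% of patients in each state and continues: "we need to analyse a total of 410 patients for remission, thus we need to include 450 patients". It shows no formula and gives no unit for the precision; it cites only an online calculator.

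The Planned analyses section then says how the cut-offs will be obtained: "Cutoff values for each outcome and for each change in outcome will be calculated using ROC curves and 75th percentile analyses". For the ROC curves it names Youden's statistic, "but also using a fixed specificity number (80%) since specificity is more important than sensitivity in this case". It describes the percentile method as one that "finds the value above which, 75% of patients reporting an outcome or a change in outcome, are placed". It mentions no confidence interval for any cut-off.

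**The concern.** Precision is the only criterion offered for the sample size; there is no hypothesis test or power statement. An interval of ±0.05 around an estimate with an SD of 2.30 needs thousands of observations, so 82 looked wrong by about two orders of magnitude.

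The study's product is a set of cut-offs meant for treat-to-target care and for interpreting other studies. A reader who takes 0.05 at face value would think the PsAID cut-offs about ten times more precise than even a mean from 82 patients. Because no intervals are planned, the reported results would not correct that impression.

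**Working it through.** **Inputs, all from the Sample size section:** SD 2.30; confidence 0.95, taken as two-sided (z = 1.96); precision d = 0.05, taken as the half-width of the interval in PsAID points; 82 patients in the state; 20% of patients in the state; 410 analysed; 450 included.

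**The plan's figure.** For a single mean, n = (z × SD/d)².

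- d = 0.05: (1.96 × 2.30/0.05)² = 8,128.8, so 8,129.
- d = 0.5: (1.96 × 2.30/0.5)² = 81.3, so 82. This is the plan's number.

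**The reverse check.**

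- Half-width with 82 patients: 1.96 × 2.30/√82 = 0.498 (0.505 with the t distribution). The ratio to the printed figure is 0.498/0.05 = 9.96.
- SD at which 82 patients would give 0.05: 0.05 × √82/1.96 = 0.231, a tenth of the stated SD.

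**Other readings of 0.05.** None returns 82.

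| Reading | n |
|---|---|
| One-sided 95% | 5,725 |
| 2.30 is a variance | 3,535 |
| 0.05 is the full interval width | 32,515 |
| 0.05 is a fraction of the SD | 1,537 |
| Proportion of 0.2, precision 0.05 | 246 |
| Proportion of 0.5, precision 0.05 | 385 |

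**The later steps.** 82/0.20 = 410. 410/450 = 0.911, an allowance of about 9% for unusable forms. Both fit d = 0.5. With d = 0.05 the number analysed would be 8,129/0.20 = 40,645, which is plainly not what was meant.

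**From a mean to a cut-off (illustration only).** The documents give neither the shape of the PsAID distribution nor its SD within a state. The figures below assume an SD of 2.30 in each group, 82 patients in the state and 410 − 82 = 328 not in it. They are 95% half-widths in PsAID points.

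| Estimate | Assumption | Half-width |
|---|---|---|
| Mean | none on shape | 0.50 |
| Either quartile | normal: 1.96 × √(0.75 × 0.25/82) × 2.30/φ(0.674) | 0.68 |
| Cut-off at 80% specificity | normal: 1.96 × √(0.8 × 0.2/328) × 2.30/φ(0.842) | 0.36 |
| Youden cut-off | normal, group means 1, 2, 3 or 4 points apart (simulated) | 1.82, 1.26, 1.04, 0.93 |
| Lower quartile | right-skewed gamma, shape 1, 1.5 or 2 (simulated) | 0.29, 0.37, 0.41 |
| Upper quartile | same | 0.85, 0.84, 0.82 |

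Repeating the Youden simulation with SDs of 1.0 and 2.0 gives 12 scenarios in all. The Youden half-width was about 1.7 to 3.7 times that of the mean in every one. The other estimators fall on either side of 0.5, depending on the method, the quartile used and the shape of the distribution.

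**The case against.** The strongest objection concerns the unit. Because none is given, 0.05 might mean 5% of a 0–10 scale. That is 0.5 points and returns exactly 82, so only a label would be missing. The reading is plausible, but the section mentions no percentage and the documents give no range for PsAID; they give 0–10 for patient global assessment and pain. Even if that was the intention, a reader cannot recover it from the text, and the sentence still needs correcting.

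It can also be said that this is probably a slip of one decimal place. No enrolment number, cut-off or planned analysis uses the 0.05, and 450 follows correctly from 82. That stands. It bears on how cheap the repair is, and it is why 8,129 should not be read as a recruitment target.

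Thirdly, the mismatch between a mean and a cut-off is a criticism of the justification, not an arithmetic error, and the illustrative half-widths rest on assumptions from outside the documents. Both statements are fair. Read literally, the plan's description of the percentile method points to the lower quartile, and with right-skewed scores that is estimated more tightly than the mean. The illustration therefore does not show that the cut-offs are less precise than ±0.5. It shows that ±0.5 does not describe them.

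Finally, ±0.5 should not be carried over to flare. Flare cut-offs are for change between visits, and the documents do not say that 2.30 is an SD of change. The section itself accepts a smaller flare sample, and the Budget section expects 400 second visits, of which 20% is 80. This limits what the corrected sentence should claim.

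**Conclusion.** The statement is wrong as written. With an SD of 2.30 and 95% confidence, a precision of 0.05 PsAID points needs 8,129 patients in the state, and 82 patients give ±0.498 for a mean, 9.96 times the printed figure. This rests only on the stated inputs and on reading precision as a half-width in PsAID points; the alternatives in the table do not rescue it. The most likely error is in the printed precision or its missing unit, not in the number of patients, and nothing here shows that 450 is too few.

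The secondary point also holds: the calculation is for a mean, while the stated purpose and the planned analyses concern cut-offs. How precise those will be cannot be settled from the documents. The half-widths for them are conditional on the assumed distributions, SDs and group differences.

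**What to change.** In the Sample size section, confirm the intended precision and its unit, and replace the figure of 0.05 with a sentence such as:

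> For remission, 82 patients in the state give a 95% half-width of about 0.5 PsAID points for the mean, assuming an SD of 2.30 within the state; this is not the precision of the percentile or ROC cut-offs.

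For flare, either give an SD of the change score and the half-width that follows from it, or state that no precision target is set.

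In the Planned analyses section, add that every cut-off will be reported with a 95% confidence interval, for example by bootstrap.

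The cost is a short text change and a little more analysis work. The stated precision becomes about ten times less favourable. Enrolment and the planned cut-off methods do not change.

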### Physician data regarding disease activity including physical examination

Physicians will fill in all the information necessary to calculate the following composite scores: DAPSA remission, DAPSA Low Disease Activity (using both DAPSA and c-DAPSA), PASDAS remission, AMDF modified remission, MDA and its several versions including MDA where both joint measures are mandated, MDA where the skin measure is mandated, MDA where these three are mandated and Very Low Disease Activity (VLDA) corresponding to all MDA criteria fulfilled. (Schoels 2015, Smolen2015, Mumtaz2011, Helliwell2014, Coates2010, Coates2016a, Coates2016d)

This includes a physical assessment with 66 swollen joint counts, 68 tender joint counts, tender enthesal points (Leeds Enthesitis Index), body surface area of psoriasis and physician global assessment. Weight and height will also be collected.

Physicians will also answer general questions on their gestalt on the disease status (remission/low disease activity or flare, please see above). To better understand the reasoning of the physician, specific questions related to the perceived cause of current symptom levels will also be asked: causality of patient symptoms between disease activity, sequels of disease or comorbidities. (as was the case in a recently-completed study in spondyloarthritis, Dougados 2017)

Here we are using a modified AMDF with no PASI replaced with skin global assessment and body surface area, to facilitate feasibility of data collection in rheumatology clinics. Furthermore the PsA Quality of Life score which is part of AMDF will not be collected: thus this is a modified AMDF. (McKenna2004, Mease2016)

We are aware we will not be collecting the data needed to calculate the Composite Psoriatic Disease Activity Index (CPDAI) for feasibility reasons. However a modified CPDAI may be calculated based on available data.

We will avoid circularity by not calculating the composite scores in the CRF.

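### One requirement of 82 patients is stated for every remission definition and for flare, but the plan's inputs do not justify it for the stricter MDA versions or for flare

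*Combined protocol and SAP*

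**What the plan says.** The Sample size section of the combined protocol and SAP sizes the study on a PsAID cutoff. The spread is taken from an earlier study: "With a standard deviation of 2.30 as observed in the PsAID development study on 107 and 475 patients". Confidence is set at 95% and the precision is printed as 0.05. The number that results is 82, and the section says that it applies to remission "whatever the remission definition) or in flare". The step to a total rests on one proportion: "we expect around 20% of patients to be in remission in this usual practice cohort". The only figure offered beside that 20% is an MDA rate of 40-50% in trials of biologics. The result is 410 analysed and 450 included. The same section assumes 20% in flare, says that the flare sample will be somewhat smaller, calls that analysis exploratory and accepts the size.

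The Background defines MDA as meeting 5 of 7 criteria. The section on physician data regarding disease activity adds versions in which the joint measures, the skin measure, or all three must be met, and "Very Low Disease Activity (VLDA) corresponding to all MDA criteria fulfilled". Table 2 has a gold-standard row for modified MDA versions and a PsAID column. The physicians' perspective list under Outcomes and planned analyses classes these versions as sensitivity analyses.

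For flare, Obtaining cutoffs specifies "changes in scores between the 2 visits for flares", and Planned analyses restricts the analysis to patients with both visits. The Budget expects 450 first and 400 second visits.

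**The concern.** A single SD, precision and proportion are made to serve every reference definition. That is a claim about each row of Tables 2 and 3, and the inputs do not reach all of them. Definitions that only add conditions to MDA cannot have more patients than MDA. A cutoff for change depends on the spread of change, which is a different quantity from the spread of a level score.

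The cutoffs are what the study is meant to deliver. A reader who takes the section at its word would give a VLDA-based or flare-based PsAID cutoff the same precision as the MDA-based one, and the plan offers no basis for that.

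**Working it through.** **Inputs.** SD 2.30, confidence 95% (taken as two-sided), precision printed as 0.05, 82 required, 20% in each state, 410 analysed, 450 included (all Sample size); 400 second visits (Budget). The documents give no proportion for each definition, no SD of change and no between-visit correlation. Values used for these are assumptions.

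**1. The plan's own figure.** No formula is printed. The precision of a single mean gives n = (1.96 × SD / d)².
- d = 0.05: (1.96 × 2.30 / 0.05)² = 8,128.5, so 8,129.
- d = 0.05 × SD = 0.115: 1,537.
- d = 0.5: 81.3, so 82.

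Of these readings only d = 0.5 returns 82, so it is used below. The later steps reproduce: 82 / 0.20 = 410, and 1 − 410/450 = 8.9% is left for unusable records.

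**2. Stricter MDA versions.** With MDA at 20%, 410 × 0.20 = 82, so there is no margin. Let f be the share of MDA patients who also meet the stricter version. The count is 82f and the half-width is 1.96 × 2.30 / √(82f), with the SD kept at 2.30.

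| f (assumed) | Patients | Half-width |
|---|---|---|
| 1.0 (MDA itself) | 82 | 0.50 |
| 0.9 | 74 | 0.52 |
| 0.7 | 57 | 0.60 |
| 0.5 | 41 | 0.70 |
| 0.3 | 25 | 0.91 |

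A strict subset can still reach 82 in two ways:
- MDA is more common than 20%. The share needed is f = 82 / (410 × MDA proportion): 67% at 30% MDA, 50% at 40%, 40% at 50%.
- All 450 are analysable. MDA at 20% then gives 90, and the subset must hold 82/90 = 91% of them.

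**3. Flare.** If the SD is 2.30 at both visits and the correlation between them is r, the SD of change is 2.30 × √(2(1 − r)). The number needed for ±0.5 is then 81.3 × 2(1 − r). Flares available: 400 × 0.20 = 80, for which the half-width is 1.96 × SD of change / √80.

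| r (assumed) | SD of change | Needed for ±0.5 | Half-width with 80 flares |
|---|---|---|---|
| 0.3 | 2.72 | 114 | 0.60 |
| 0.5 | 2.30 | 82 | 0.50 |
| 0.7 | 1.78 | 49 | 0.39 |
| 0.8 | 1.45 | 33 | 0.32 |

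The plan's 82 corresponds to r = 0.5, which it does not state. The 80 is before unusable records and before patients with very high initial values are set aside, as Planned analyses intends. A further loss of 10, 20 or 30% would leave 72, 64 or 56.

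**4. What the formula covers.** It gives the precision of a mean. The planned cutoffs come from ROC curves and the 75th percentile. For a 75th percentile under normality, the variance ratio to a mean is 0.75 × 0.25 / φ(0.674)² = 1.86, so ±0.5 would take about 81.3 × 1.86 = 151 patients. The half-widths above therefore compare rows on the plan's own basis; they are not the precision of the cutoffs.

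**The case against.** A reader might infer that 82 cannot hold for these rows. That goes too far. The number required depends on SD and precision, not on prevalence; being a subset affects only how many patients are available. The section never says that MDA itself will be 20%, and the trial figure beside it is 40-50%, at which a version holding half of the MDA patients would supply 82 to 102. The SD within a VLDA group could also be below 2.30, since VLDA requires low pain, low patient global and low HAQ together, so the half-widths for the stricter rows may be overstated.

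A reader might also infer that flare is undersized. The documents do not support that either. At r above 0.5, 82 is more than enough, and 80 flares against 82 moves the half-width only from 0.498 to 0.504 at SD 2.30. The section openly accepts a smaller flare sample and labels the analysis exploratory, and the modified MDA rows are sensitivity analyses.

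All of this stands, and it limits the point to one of justification and of low severity. It does not remove the point. If each definition needs 82, then 410 is enough only for definitions with at least 20% prevalence, and the plan shows this for none of the stricter versions. The remark on flare concerns the count, is not quantified, and says nothing about the SD of change.

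**Conclusion.** The concern holds in limited form: the stated size is not justified for the stricter MDA versions or for flare. It is not shown to be wrong for them.

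If MDA is 20% of 410, every strict subset falls below 82; the counts of 41 and 25 rest on assumed shares, and their half-widths on an SD of 2.30 within the subset. For flare, the direction of the error is unknown without an SD of change. All of this takes the precision as 0.5; the printed 0.05 is inconsistent with 82 and has to be corrected in the same sentence.

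Severity is minor. The affected rows are sensitivity or exploratory analyses, and neither enrolment nor study procedures depend on the answer.

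**What to change.** In Sample size:
- Delete the parenthesis that extends the requirement to any remission definition.
- State that 82 and 410 apply to MDA, on PsAID level, at 20% prevalence, with a precision of 0.5 in place of the printed 0.05.
- Give expected counts and precision for the stricter MDA versions, saying that they fall below 82 under the same assumption.
- For flare, give an SD of change with its assumed range, and about 80 expected flares from 400 second visits.
- Say that the formula is for a mean, so that its half-widths are not read as the precision of the cutoffs.

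In Planned analyses, report a confidence interval (for example by bootstrap) with each ROC and 75th-percentile cutoff. This shows the precision actually achieved in each row. A rule that relabels rows below 82 as descriptive would be arbitrary and is not needed.

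The cost is wording, a short table and the interval computation. The downside is that the stated precision becomes less favourable for the stricter definitions.
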